1.1.5.2. Pharmacokinetics

Based on preclinical data, the following are the predicted characteristics in humans:

- Low-to-moderate oral bioavailability
- Projected half-life of approximately 2 hours
- Once daily dose of 400 to 800 mg is expected to achieve target plasma exposures associated with antitumor activity

- Reduced solubility of BDTX-189 at increasing pH may result in decreased exposures with concomitant use of acid-reducing agents and food
- Plasma protein unbound fraction: 1.5%
- Metabolized mainly by CYP3A4, with multiple alternative pathways and glutathione conjugation; no CYP-mediated perpetrator drug interactions expected. However, the use of strong CYP3A inhibitors and inducers with BDTX-189 is prohibited.
- BDTX-189 is a substrate of P-glycoprotein (P-gp) and breast cancer resistance protein (BCRP) and coadministration with strong inhibitors of P-gp or BCRP should be used with caution. BDTX-189 is a moderate inhibitor of BCRP and sensitive substrates should be used with caution.
- Negligible excretion in urine as parent

1.1.6. Toxicology

The rat and dog were chosen as appropriate toxicology species based on the comparative metabolic profiling of BDTX-189 in the liver microsomes and hepatocytes of rats, dogs, and humans.

In the definitive good laboratory practice (GLP) study, following oral administration of BDTX - 189 QD over a period of 28 days to male and female rats, the highest non-severely toxic dose (HNSTD) was 30 mg/kg/day. This was based on BDTX-189-related clinical signs observed at 60 mg/kg/day in females, including body weight loss, piloerection, hunched posture, and reduced food intake. Males tolerated daily administration of 60 mg/kg/day for the full 28-day dosing period, but food intake was slightly lowered during the first week of treatment and the overall body weight gain was 27% less than that of concurrent controls. There were no BDTX-189-related clinical signs at 10 or 30 mg/kg/day. There were no effects on urinalysis and organ weights, nor were there ocular changes or effects on functional/behavioral observation parameters at any dose level. Microscopic changes considered related to treatment consisted of slight and reversible inflammation and hyperplasia of the mucosa in various regions of the gastrointestinal tract at all dose levels, and at the mid- and high dose levels were accompanied by elevated total white blood cell (WBC) counts (primarily neutrophils). Following a 14-day recovery period, inflammation in the gastrointestinal tract and WBC counts were completely reversed.

In the definitive GLP study, following oral administration of BDTX-189 BID over a period of 28 days to male and female dogs, the 20 mg/kg BID dose level (40 mg/kg/day) was poorly tolerated, with marked clinical signs, inappetence, and weight loss necessitating the premature termination of one animal on Day 17. Dose levels of 10 and 20 mg/kg/day were well tolerated. Based on in-life and pathology findings, the HNSTD was 20 mg/kg/day (10 mg/kg BID). Microscopic findings were consistent with a primary irritant effect to the proximal gastrointestinal tract, with associated secondary changes within the mesenteric lymph node and pancreas. Secondary changes noted in mesenteric lymph node consisted of increased sinus erythrocytes, a reaction to the gastrointestinal effect, and was not noted in other peripheral lymph nodes. In the pancreas, only edema was noted without any evidence of degeneration or inflammation. Slight inflammation of the renal papilla in one animal administered 40 mg/kg/day was of uncertain

pathogenesis and its relationship to BDTX-189 is uncertain. Complete or partial reversibility was demonstrated following the 14-day treatment-free period, with the exception of the duodenal glandular dilatation, which would be expected to resolve over a longer recovery period.

BDTX-189 did not show effects on cardiovascular or respiratory function in GLP safety pharmacology studies in dog and rat, respectively. BDTX-189 was not an inhibitor of human ether-à-go-go related gene (hERG) at concentrations up to and including 7.5 μ M. BDTX-189 did not show evidence of phototoxic potential *in vitro*. BDTX-189 did not show evidence of mutagenicity or clastogenicity in *in vitro* GLP genotoxicity assays.

1.1.7. Clinical Experience

As of 02 April 2021, preliminary safety data were available for 65 patients from Part A of this study who have received at least 1 dose of BDTX-189, including 55 patients who were administered a QD schedule with doses including 25 to 200 mg (n=5, fasting), 400 mg (n=7, fasting), 800 mg (n=21, fasting), 800 mg (n=9, non-fasting [NF]), 1000 mg (n=7, NF), 1200 mg (n=6, fasting). A total of 10 patients have received the BID schedule, with doses of 600 mg (n=5, NF) and 800 mg (n=5, NF).

The DLT-evaluable population consisted of 45 patients who were enrolled into the dose-escalation cohorts. No DLTs have been reported with doses of 800 mg BDTX-189 QD (fasting or NF) or less in the dose escalation cohorts. The MTD was exceeded with 2 patients in each of the cohorts receiving either 1200 mg QD (fasting) or 1000 mg QD (NF). The 800 mg QD, NF dose was considered the MTD and the recommended phase 2 dose (RP2D). The 800 mg and 600 mg BID fasting doses also exceeded the MTD with 3 patients each experiencing DLTs. A cohort evaluating 400 mg BID, NF is currently enrolling.

The majority of DLTs were gastrointestinal in nature with diarrhea reported in 6 patients, vomiting in 5, and nausea in 4. Other DLTs reported by 1 patient included increased alanine aminotransferase (ALT) with or without increased aspartate aminotransferase (AST), increased bilirubin, increased creatinine, and dehydration. Some patients experienced more than 1 DLT, and these were either Grade 2 or 3 severity.

[figure not shown]
The most frequently reported treatment-emergent adverse events (TEAEs) were diarrhea (58.5%), nausea (47.7%), vomiting (44.6%), fatigue (29.2%), and increased ALT (23.1%). No dose relationship was observed in TEAEs reported. The majority of the TEAEs were Grade 1 or 2 (mild or moderate) with 43.1% of patients reporting TEAEs of Grade ≥ 3 . The most frequently reported TEAEs Grade ≥ 3 included diarrhea (15.4%) and increased ALT (7.7%); all were considered by the Investigator to be related to the study treatment.

Preliminary PK data available for 43 patients showed oral absorption was generally rapid. In the multiple patient cohorts, there were dose-dependent increases in exposure (i.e., maximum concentration [C_{max}] and area under the plasma concentration-time curve [AUC]) seen with single (C1D1) and multiple (C1D15) daily administrations up to 800 mg, before an exposure plateau was reached at 1200 mg (see [Figure 8](#)). Exposures at 800 mg QD were approximately 1.5-fold lower than projected from preclinical data. The median elimination half-life ($t_{1/2}$) across all dose levels ranged from 2.2 to 5.9 hours, which is in line with preclinical projections of approximately 2 hours. No consistent trend of accumulation or decreasing exposures on multiple dosing was indicated. In the ongoing Food Effect cohorts, evaluating the effect of a high-fat or

low-fat meal on the PK of BDTX-189, 6 patients are considered evaluable in each cohort. The effect of a high-fat meal on the PK of BDTX-189 suggests a slightly positive effect of food with geometric mean ratio for C_{max} and AUC_{0-t} of 1.0 and 2.3 respectively. Administration of BDTX-189 with food resulted in an approximately 2.5-fold increase in median t_{max} (median t_{max} 1.5 hours fasted, 3.5 hours low-fat meal, 4.0 hours high-fat meal) relative to administration in the fasted state, and no change in median $t_{1/2}$.

Based on the results described above, the Safety Review Committee (SRC) recommended that the remaining patients to be enrolled will be administered BDTX-189 following consumption of a meal (i.e., NF).

Figure 8 Relationship Between BDTX-189 Dose (mg/day QD) and Exposure (C_{max} and AUC_{0-t})

AUC_{0-t} =area under the plasma concentration-time curve from time 0 to the time of the last measurable concentration;
 C_{max} =maximum concentration.

1.1.8. Study Rationale and Rationale for Starting Dose

Allosteric mutations in [REDACTED] and [REDACTED] have been identified and characterized; these mutations encode molecular changes in these oncogenic targets that are not located at traditional substrate or inhibitor binding sites, but rather act at a distance to influence the binding properties of these sites. BDTX-189 is highly potent against these allosteric mutations which are found in 1% to 2% of a large variety of solid tumors but are enriched in tumors such as advanced NSCLC, invasive breast cancer, bladder cancer, and endometrial cancer. Currently available [REDACTED] and [REDACTED] TKIs or mAbs have limited or no antitumor activity against these genetic alterations either because of insufficient potency or lack of selectivity which results in toxicity before adequate exposures are achieved. Therefore, there is a high unmet medical need for a large group of patients currently not served. The goal of the development plan for BDTX-189 is to efficiently evaluate the antitumor activity across a broad range of solid tumor types expressing allosteric *ErbB* mutations.

BDTX-189 binds covalently to the ATP-binding site of the mutant receptor at very low concentrations ($IC_{50} < 77$ nM cellular potency). It has been demonstrated that BDTX-189 remains bound to mutant receptors for at least 24 hours, with site occupancy >50% at 24 hours after probe addition. This observation has been confirmed *in vivo*, where oral administration of BDTX-189 to athymic nude mice bearing allosteric *ErbB* mutant BaF3 allografts showed suppression of target phosphorylation for at least 24 hours. This indicates that BDTX-189 binds

[figure not shown]
to the active site of *ErbB* allosteric mutants via a slow off-rate or covalent mechanism supporting once daily dosing in humans.

The determination of the Phase 1 starting dose in cancer patients was based on the results of the 28-day GLP toxicology studies in rat and dog. The human equivalent dose at the HNSTD in rat and dog is 180 mg/m² and 400 mg/m², respectively, and as such defined rat as the most sensitive species. The proposed maximum recommended starting dose was calculated in accordance with the International Council for Harmonisation (ICH) S9 Nonclinical Evaluation for Anticancer Pharmaceuticals (adopted by the FDA, 2010) using the toxic dose in 10% of animals (STD₁₀), which in rat was exceeded at 60 mg/kg/day and a dose of 30 mg/kg/day was the HNSTD. The starting dose was calculated as 25 mg QD as follows: 30 mg/kg/day (highest dose level < STD₁₀ in rat) × 6 (human equivalent dose mg/m² conversion) × 1/10 (rodent safety factor) × 1.62 (human body surface area), and rounded down to the nearest multiple of 5.

With a starting dose of 25 mg QD and the projected dose to achieve exposures associated with antitumor activity in humans being 400 to 800 mg QD (see Section 1.1.5.2), this justifies using single-patient cohorts during the accelerated titration with doubling dose increments until a ≥ Grade 2 AE related to BDTX-189 is observed, or until the 200 mg QD dose cohort is complete (see Section 4.3). The projected dose range expected to be associated with antitumor activity in humans is 6.7-13 mg/kg/day which compares favorably with the HNSTD of 20 and 30 mg/kg/day observed in dog and rat, respectively.

Given that the mechanism of action of BDTX-189 is covalent/irreversible, the totality of emerging PK/PDx data will need to be considered in a scenario where the half-life is too short to achieve sufficient target engagement/pathway modulation, or where target coverage is under predicted in preclinical models (Figure 9). Therefore, a parallel Dose Escalation of one alternative dose schedule (BID) of BDTX-189 may be evaluated.

Figure 9 Predicted BDTX-189 Unbound Plasma Concentrations over Time for QD and BID Dosing Schedules

1.2. Potential Risks and Benefits of the Treatment Regimen

This is the first in-human study with BDTX-189. The risks for human patients have been estimated based on the results of the preclinical toxicology studies with BDTX-189.

The target organs of toxicology with BDTX-189 based on preclinical data include:

- Gastrointestinal Effects: Inflammation/hyperplasia/atrophy of the gastrointestinal mucosa (esophagus, stomach, duodenum, jejunum, ileum, cecum) consistent with a primary irritant effect in the proximal gastrointestinal tract in dogs with associated secondary changes within the mesenteric lymph nodes and pancreas, increases in total WBC in both species and increases in platelet counts in dogs at the higher dose levels. This was associated with clinical signs of inappetence, vomitus, and liquid/loose feces in rat and/or dog. All of these BDTX-189-related findings completely or partially resolved following a 14-day recovery period.

Toxicology findings of uncertain relationship to BDTX-189 include:

- Kidney: Slight papillary inflammation of unknown pathogenesis in 1 dog at 40 mg/kg/day.
- Pancreas: Minimal-to-slight interstitial edema in dogs at 20 and 40 mg/kg/day considered secondary to gastrointestinal inflammation.

Adverse events observed in the dose-escalation portion of the ongoing Phase 1 study:

- Gastrointestinal disorders including nausea, vomiting and diarrhea, some at Grade 3 severity
- Hepatic test abnormality, including Grade 3 ALT and/or AST elevations and Grade 2 blood bilirubin elevation

Despite the 6-fold *in vitro* selectivity of BDTX-189 for *ErbB* mutations versus WT [REDACTED], the potential for typical [REDACTED]-related class AEs such as cutaneous toxicities and diarrhea cannot be excluded. Moreover, due to the potent anti-[REDACTED] effects the potential for cardiac dysfunction is a theoretical possibility. The potential risks associated with BDTX-189 treatment based on observed toxicology findings and potential class-effects are considered monitorable and reversible in patients. Please refer to the BDTX-189 IB for further details regarding the potential risk associated with the use of BDTX-189.

Patients will be monitored periodically as per the Schedule of Assessments ([Table 1](#), [Table 2](#), and [Table 3](#)) with physical examinations, hematology, chemistry, coagulation, urinalysis, electrocardiograms (ECGs), and cardiac function. Women of child-bearing potential (WOCBP) and male patients must agree to use a highly-effective method of contraception during the study and for at least 90 days after the last dose of study treatment.

Currently, [REDACTED]-directed therapies are only approved for patients with tumors harboring [REDACTED] amplifications and not for [REDACTED] mutations. Allosteric *ErbB* mutations are mostly resistant to approved [REDACTED]-directed therapies at achievable systemic exposures in humans. There remains a significant unmet medical need for drugs that target allosteric *ErbB* mutations including [REDACTED]. The preclinical data for BDTX-189 demonstrate antitumor activity across a range of allosteric *ErbB* mutants both *in vitro* and *in vivo* evidenced by both TGI and regression. The data obtained to date for BDTX-189 are regarded as sufficient to justify evaluation of the objectives for the planned study in patients with advanced solid malignancies. BDTX-189 is an investigational drug and currently there are no proven benefits.

1.2.1. Precautions and Risks Associated with BDTX-189

Dose-limiting toxicities have included reversible Grade 3 ALT/AST increases, Grade 3 diarrhea (lasting >24 hours), Grade 3 dehydration, and intolerable Grade 2 and Grade 3 nausea and vomiting. Gastrointestinal disorders increased in frequency and severity with increasing doses. A total of 72% of the patients across all dose levels experienced treatment-related gastrointestinal TEAEs, of which 19% were Grade 3 severity. A total of 14% experienced a drug-related skin disorder TEAE. No patients have experienced a treatment-related TEAE of Grade 4 or 5 severity. Further details are described in the IB.

2. STUDY OBJECTIVES AND ENDPOINTS

2.1. Primary Objective

The primary objectives of this study are to:

Part A

- Determine the recommended Phase 2 dose (RP2D) and schedule of BDTX-189 as a single agent administered orally (PO) in patients with advanced solid malignancies.

Part B

- Assess the antitumor activity of BDTX-189 as a single agent in patients with allosteric mutations, including [REDACTED] mutations.

2.2. Secondary Objectives

The secondary objectives of this study are to:

Part A and B

- Assess the safety and tolerability of BDTX-189 as a single oral agent.
- Investigate the PK of BDTX-189 using population PK (PopPK) methods and explore correlations between PK, response, and/or safety findings.

Part A

- Establish the PK of BDTX-189 and circulating metabolite profile after a single dose and at steady state.
- Assess the preliminary efficacy and antitumor activity of BDTX-189 as a single oral agent.
- Assess the effect of food on the PK of BDTX-189.

Part B

- Assess additional measures of efficacy and antitumor activity of BDTX-189 as a single agent.
- Assess patient outcome by evaluation of electronic patient reported outcomes (ePRO).

2.3. Exploratory Objectives

The exploratory objectives of this study are to:

Part A and B

- Evaluate allosteric *ErbB* mutations, gene amplifications, and possible markers of drug sensitivity and resistance in plasma using ctDNA.

Part A

- Evaluate the PDx effects of BDTX-189 in tumor tissue as determined by *ErbB* signaling pathway proteins.

2.4. Endpoints

The study endpoints are provided in [Table 4](#).

Table 4 Study Objectives and Corresponding Endpoints

Primary Objective:	Endpoint/Variable:
Part A: Determine the RP2D and schedule of BDTX-189 administered PO in patients with advanced solid malignancies	Incidence and severity of TEAEs, including DLTs, graded according to NCI CTCAE, Version 5.0
Part B: Assess the antitumor activity of BDTX-189 as a single agent in patients with allosteric [REDACTED] mutations, including [REDACTED] mutations	Objective response defined as either a CR or PR, as determined by BICR and per RECIST version 1.1 based on CT or MRI scans
Secondary Objectives:	Endpoint/Variable:
Part A and B: Assess the safety and tolerability of BDTX-189 as a single oral agent	Incidence of TEAEs; changes in clinical laboratory parameters, vital signs, ECG parameters, cardiac function, and physical examination results
Part A and B: Investigate the PK of BDTX-189 using PopPK methods and explore correlations between PK, response, and/or safety findings	PopPK parameters: Cl/F, Vd/F, and Ka for BDTX-189. Cl/F will be used to generate estimates of BDTX-189 AUC. Possible PK/safety and PK/efficacy correlations, and covariate analysis of intrinsic/extrinsic factors
Part A: Establish the PK of BDTX-189 and circulating metabolite profile after a single dose and at steady-state	PK parameter estimates of BDTX-189 generated from plasma concentration-time data (e.g., C_{max} , T_{max} , AUC, and $t_{1/2}$)
Part A: Evaluate the preliminary efficacy and antitumor activity of BDTX-189 as a single oral agent	Investigator-assessed objective response, DOR, DCR, PFS as determined by RECIST v1.1, and OS (for Safety Expansion portion).
Part A: Assess the effect of food on the PK of BDTX-189	PK parameter estimates of BDTX-189 generated from plasma concentration-time data (e.g., C_{max} , T_{max} , AUC, $t_{1/2}$, Cl/F, and Vd/F). Fed/fasted geometric least squares mean ratio and 90% CI for BDTX-189 C_{max} and AUC
Part B: Assess additional measures of efficacy and antitumor activity of BDTX-189 as a single agent	Objective response (Investigator assessed), DOR (Investigator and BICR assessed), DCR (Investigator and BICR assessed), PFS (Investigator and BICR assessed) per RECIST v1.1, and OS
Part B assess patient outcome by evaluation of PROs	Change from baseline in the FACT-G subscales, NCCN-FACT FBSI-16 subscales, NCCN-FACT FLSI-17 subscales, EQ-5D-5L, PROMIS physical function score, and NCI-CTCAE scores
Exploratory Objectives:	Endpoint/Variable:
Part A and B: Evaluate allosteric ErbB mutations, gene amplifications, and possible markers of drug sensitivity and resistance in plasma using ctDNA	Presence and/or disappearance of [REDACTED] ErbB mutations and other [REDACTED] mutations, and other markers of drug sensitivity and resistance

Primary Objective:	Endpoint/Variable:
Part A: Evaluate the PDx effects of BDTX-189 in tumor tissue as determined by ErbB signaling pathway proteins	ErbB signaling pathway proteins in tumor tissue, such as pERK

Abbreviations: AUC = area under the concentration time curve; BICR = blinded independent central review; CI = confidence interval; Cl/F = oral clearance; C_{max} = maximum concentration; CR = complete response; CT = computed tomography; CTCAE = Common Terminology Criteria for Adverse Events; ctDNA = circulating tumor DNA; DCR = disease control rate; DLT = dose limiting toxicity; DOR = duration of response; ECG = electrocardiogram; [REDACTED]; ePRO = electronic patient reported outcomes; EQ-5D-5L = EuroQol Group's 5-domain 5-level questionnaire; FACT = Functional Assessment of Cancer Therapy; FACT-G = Functional Assessment of Cancer Therapy-General; FBSI = Functional Assessment of Cancer Therapy Breast Symptom Index; FLSI = Functional Assessment of Cancer Therapy Lung Cancer Symptom Index; [REDACTED] Ka = first-order absorption rate constant; MRI = magnetic resonance imaging; NCCN = National Comprehensive Cancer Network; NCI = National Cancer Institute; OS = overall survival; PDx = pharmacodynamics; pERK = phosphorylated extracellular regulated kinase; PFS = progression-free survival; PK = pharmacokinetics; PO = by mouth; popPK = population pharmacokinetics; PR = partial response; PROMIS = Patient Reported Outcomes Measurement Information System; RECIST = Response Evaluation Criteria in Solid Tumors; RP2D = recommended Phase 2 dose; t_{1/2} = elimination half-life; TEAEs = treatment-emergent adverse events; T_{max} = time for maximum concentration; Vd/F = oral volume of distribution.

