Mutations must have been determined by a validated NGS test routinely used by each institution using tissue and/or plasma and performed in a CLIA-certified or equivalent laboratory. A list of eligible validated oncogenic mutations from 1 of the 7 MTCs is provided in [Appendix I](#).

Eligible patients will be assigned to one of the 5 following cohorts:

Cohort 1: NSCLC with an [REDACTED] mutation from MTC-A.

Cohort 2: NSCLC with an [REDACTED] mutation from MTC-B or point mutation from MTC-C.

Cohort 3: Breast cancer with an [REDACTED] mutation from MTC-B, MTC-C, MTC-D, MTC-E, or MTC-F.

Cohort 4: NSCLC, biliary tract cancer, or cervical cancer with an [REDACTED] mutation from MTC-D.

Cohort 5: Any solid tumor type with any allosteric *ErbB* mutation from any of the 7 MTCs (MTC-A to MTC-G), excluding patients who are otherwise eligible for Cohorts 1-4.

Note: The Sponsor reserves the right to prioritize Cohorts (ie, tumor/mutation pairs) and to cap enrollment for any Cohort based on the Sponsor's portfolio decision-making process.

17. Measurable disease according to RECIST version 1.1 ([Appendix B](#)).

18. Mandatory archival tumor tissue or willing to undergo pretreatment biopsy if no archival tissue available (Section [5.7.1](#)).

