10.3.3. Blinded Independent Central Review Committee

A blinded independent central review (BICR) committee will review all available tumor assessment scans for patients enrolled to Part B of this study. Each image will be independently reviewed. The process for review and adjudication of the images will be provided in the imaging review charter (IRC).

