Appendix B Response Evaluation Criteria in Solid Tumors (RECIST) Version 1.1

Definitions

Response and progression will be evaluated in this trial using the RECIST v1.1 ([Eisenhauer et al. 2009](#)). Lesions are either measurable or non-measurable using the criteria provided below. The term “evaluable” in reference to measurability will not be used, as it does not provide additional meaning or accuracy.

Baseline Eligibility

Measurable Disease:	
Tumor lesions: Must be accurately measured in at least one dimension (longest diameter in the plane of measurement is to be recorded) with a minimum size of:
 
• 10 mm by CT by computed tomography (CT scan slice thickness no greater than 5 mm).• 10 mm caliper measurement by clinical exam (lesions that cannot be accurately measured with calipers should be recorded as non-measurable).• 20 mm by chest x-ray. 
Skin lesions: Documentation by color photography, including a ruler to estimate the size of the lesion, is recommended.
 
Malignant lymph nodes: To be considered pathologically enlarged and measurable, a lymph node must be ≥ 15 mm in short axis when assessed by CT scan. At baseline and in follow-up, only the short axis will be measured and followed.

Non-Measurable Disease:	All other lesions, including small lesions (longest diameter <10 mm or pathological lymph nodes with ≥ 10 - to <15 -mm short axis) as well as truly non-measurable lesions. Lesions considered truly non-measurable include: leptomeningeal disease, ascites, pleural or pericardial effusion, inflammatory breast disease, lymphangitic involvement of skin or lung, abdominal masses, and abdominal organomegaly identified by physical exam that is not measurable by reproducible imaging techniques.

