Target Lesions:	
The most reproducible measurable lesions, up to a maximum of 2 lesions per organ and 5 lesions in total, representative of all involved organs should be identified as target lesions and recorded and measured at baseline.
 
Target lesions should be selected on the basis of their size (lesions with the longest diameter), should be representative of all involved organs, and in addition should be those that lend themselves to reproducible repeated measurements. Pathological nodes which are defined as measurable and that may be identified as target lesions must meet the criterion of a short axis of ≥ 15 mm by CT scan.
 
A sum of the diameters (longest for non-nodal lesions, short axis for nodal lesions) for all target lesions will be calculated and reported as the baseline sum diameters. If lymph nodes are to be included in the sum, then as noted above, only the short axis is added into the sum. The baseline sum diameters will be used as reference to further characterize any objective tumor response.

Non-Target Lesions:	
All other lesions should be identified as non-target lesions at baseline. Measurements of these lesions are not required, but the presence or absence of each should be noted throughout follow-up.

Guidelines for Evaluation of Measurable Disease

All measurements should be taken and recorded in metric notation, using a ruler or calipers. All baseline evaluations should be performed as closely as possible to the beginning of treatment, as per protocol screening requirements.

The same method of assessment and the same technique should be used to characterize each identified and reported lesion at baseline and during follow-up. Imaging-based evaluation is preferred to evaluation by clinical examination when both methods have been used to assess the antitumor effect of a treatment.

Clinical Lesions:	Clinical lesions will only be considered measurable when they are superficial (e.g., skin nodules and palpable lymph nodes) and ≥ 10 mm in diameter. In the case of skin lesions, documentation by color photography, including a ruler to estimate the size of the lesion, is recommended.
Chest X-ray:	Lesions on chest X-ray are acceptable as measurable lesions when they are clearly defined and surrounded by aerated lung. However, a CT scan is preferable.

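### Part B accepts disease measurable only by clinical examination, but the primary response is read centrally from CT or MRI, so some patients may have no central target lesion and cannot be assigned a central PR

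*Combined protocol and SAP*

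**What the plan says.** **Eligibility.** Criterion 17 in Section 3.1 asks Part B patients for "Measurable disease according to RECIST version 1.1" and points to Appendix B. The Part B list in the Synopsis has the same bullet. Neither specifies how the lesion must be measured.

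**What Appendix B counts as measurable.** The minimum sizes include "10 mm caliper measurement by clinical exam". The row on clinical lesions adds: "Clinical lesions will only be considered measurable when they are superficial", with skin nodules and palpable nodes as examples and a 10 mm threshold. For malignant nodes, the measurable-disease row asks for at least 15 mm "in short axis when assessed by CT scan", and the target-lesion row repeats that limit for any node chosen as a target.

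**The primary endpoint.** Table 4 defines it as "Objective response defined as either a CR or PR, as determined by BICR and per RECIST version 1.1 based on CT or MRI scans". Under Section 10.3.3 the central committee "will review all available tumor assessment scans for patients enrolled to Part B of this study". Appendix B recommends photographs of skin lesions, but no section says that photographs or caliper data reach the central readers. The reading process is left to a separate imaging charter.

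**Scoring.** In Appendix B a PR is a fall of at least 30% in the summed target-lesion diameters. Section 9.2 treats patients who stop assessments, progress, die or start other therapy before a CR or PR as non-responders. Section 9.5.3 does the same for those without an adequate post-baseline assessment.

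**Imaging.** Table 3 footnote s requires CT or MRI of chest, abdomen and pelvis plus other known disease sites. Section 5.3.3 asks sites only to keep chest and abdomen images available for transmission.

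**The concern.** Eligibility and the primary endpoint define assessable disease differently, and nothing in the protocol links the two. A patient can enter Part B on a caliper-measured skin lesion that a scan cannot measure. The central readers then have no diameter to sum, so the PR rule cannot be applied whatever the tumor does. The overall-response table in Appendix B has no row for a patient without target lesions. Such a patient stays in the denominator.

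The stake is a downward bias in the central ORR and a loss of power in designs that have almost none to spare: Tables 12 to 15 give type II errors of 0.1992, 0.1989, 0.1989 and 0.1982 against a nominal 0.20.

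**Working it through.** **Inputs.** Each Cohort 3 and Cohort 4 subgroup enrolls 10 patients, stops if there are no responses, otherwise enrolls 19 more, and rejects the null with at least 4 responses in 29. The null is 5% and the target 20% (Sections 9.3.2.2 and 9.3.2.3). The share f of patients with no lesion measurable on CT or MRI is not in the documents, so it is assumed.

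**Formula.** Let p be the chance that a patient counts as a responder.

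- Stop at stage 1: (1 − p)^10
- Power: P[Bin(29, p) ≥ 4] − (1 − p)^10 × P[Bin(19, p) ≥ 4]

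The subtracted term removes trials that would have reached 4 responses in stage 2 but had already stopped.

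**Reproducing the plan.** At p = 0.20, the stage 1 stop is 0.80^10 = 0.1074, and power is 0.8596 − 0.1074 × 0.5449 = 0.8011, so type II error is 0.1989. At p = 0.05, the stage 1 stop is 0.95^10 = 0.5987 and type I error is 0.0468. All agree with Tables 13 and 14. The same enumeration reproduces Table 12 (power 0.8008) and Table 15 (power 0.8018).

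**Effect of f.** Assume that the rest respond at the target rate and that affected patients never count as central responders. Then p = 0.20 × (1 − f) under the target and 0.05 × (1 − f) under the null.

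| Assumed f | p at target | Power | Type I error |
|---|---|---|---|
| 0 | 0.200 | 0.8011 | 0.0468 |
| 2% | 0.196 | 0.7882 | 0.0440 |
| 5% | 0.190 | 0.7677 | 0.0400 |
| 10% | 0.180 | 0.7298 | 0.0338 |

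As an example, f = 10% gives 0.7923 − 0.1374 × 0.4549 = 0.7298.

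**By count.** One affected patient among 29, placed at random, falls in stage 1 with chance 10/29 (leaving 9 and 19 readable patients) or in stage 2 with chance 19/29 (leaving 10 and 18). Power is 10/29 × 0.7667 + 19/29 × 0.7862 = 0.7795. Two and three such patients give 0.7558 and 0.7300.

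**Which read the interim uses.** The table applies the reduced rate at both stages. If the interim counted these patients through the Investigator read, the stage 1 stop would stay at 0.1074. Power would be P[Bin(29, p) ≥ 4] − 0.1074 × P[Bin(19, p) ≥ 4]: 0.8285 − 0.1074 × 0.5005 = 0.7748 at f = 5%, and 0.7923 − 0.1074 × 0.4549 = 0.7435 at f = 10% (from unrounded terms). Most of the loss therefore comes from the final count. Only if the interim uses the central read does the wrong stage 1 stop rise, from 0.1074 to 0.1216 (f = 5%) or 0.1374 (f = 10%).

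**Other cohorts, same assumption.** At f = 5% and 10%, power is 0.7229 and 0.6276 in Cohorts 1 and 2, and 0.7422 and 0.6707 in Cohort 5. These are illustrations; nothing in the documents suggests shares of that size there.

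**The case against.** The strongest reply is that Part B assessment is built on imaging. Table 3 schedules CT or MRI and no caliper measurement, footnote s extends the scans to other known disease sites, and Appendix B prefers imaging when both methods have been used. A superficial nodule of 10 mm or more that can be measured on such a scan can be a central target. This stands. A reader might infer that every patient with superficial disease is lost to the central PR; the documents do not support that.

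Palpable nodes of 10 to 14 mm might look like a second affected group, because the clinical-lesion row would accept them. The more specific target-lesion rule requires at least 15 mm on CT, so a node that qualifies as a target is already CT-measurable. The two rows could be reconciled, but the clear remaining case is skin disease that scans cannot measure.

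Three further inferences go too far:

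- That these patients cannot be central responders at all. A CR through disappearance of non-target disease is not excluded, so setting their response chance to zero slightly overstates the loss.
- That false futility stops rise. The Synopsis and Section 9.6.2 name no reader for the interim.
- That a gap between Investigator and central ORR is built in. Investigators work from the same scheduled scans, so a gap is possible but not established.

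Finally, the imaging charter is not among the documents and could contain rules for patients without a central target lesion. It could not change criterion 17 or the CT/MRI basis in Table 4. The mismatch in the protocol text therefore remains.

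**Conclusion.** The mismatch is real but narrow. It concerns patients whose only measurable disease is clinical and cannot be measured on CT or MRI. Followed as written, the plan admits them, leaves no route to a central PR and would usually count them as non-responders. The bias is downward. Type I error falls rather than rises, so the risk is missed activity and not false success.

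The size depends on a share that the documents do not give and that is probably small. One such patient in a 29-patient subgroup costs about 2 points of power (0.801 to 0.780). Assumed shares of 5% and 10% give 0.768 and 0.730 if the central read applies throughout, and slightly less loss if it applies only at the final analysis. It is reasonable to expect the breast cancer subgroups of Cohort 3 to be the most exposed, but that is a judgement and not a figure from the plan. The stated sample sizes and error rates are correct as calculated.

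**What to change.** In criterion 17 and the matching Part B bullet in the Synopsis, require at least one lesion measurable by CT or MRI under RECIST 1.1, and state that a lesion measurable only by clinical examination does not suffice. Criterion 14 (Safety Expansion, where response is Investigator-assessed) can stay as it is.

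In Section 5.3.3, widen the image-transmission wording from chest and abdomen to the sites in Table 3 footnote s: chest, abdomen, pelvis and other known disease sites. Otherwise a scanned superficial lesion outside the chest and abdomen may not reach the central readers.

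The cost is a short amendment with no change to any sample size or decision rule. The downside is that the few patients with only clinically measurable disease could not enter Part B, which matters where the mutation is rare. If the sponsor prefers to keep them, add a sensitivity analysis of central ORR restricted to patients with centrally measurable disease at baseline.
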